10.4.1 Discharge Assessment

On the day of discharge the following assessments will be made:

- Adverse events assessment
- Length of hospital stay

MDT17051PDS Version 4.0 Page 27 of 56

10.4.2 1-Month Follow-up (+/- 14 Days) Visit

One (1) month post-operative, assessments will take place by delegated study personnel via an on-site visit. Assessments will include:

- Hernia recurrence/reoperation
- Adverse events assessment
- Carolinas Comfort Scale™ QOL questionnaire Post-Operative assessment

(Section 17.2: Appendix B)

10.4.3 3-Month Follow-up (+/- 14 Days) Visit

Three (3) months post-operative, the following assessment will take place during a subject visit:

- Hernia recurrence/reoperation
- Adverse events assessment

10.4.4 12-Month and 24-Month Follow-up (+/- 30 Days) Visit

Twelve (12) and twenty-four (24) months post-operative, the following assessment will take place during a subject visit:

- Hernia recurrence/reoperation
- Adverse events assessment
- Carolinas Comfort Scale™ QOL questionnaire- Post-Operative assessment

(Section 17.2: Appendix B)

If at the twenty-four (24) month post-operative visit, after three (3) attempts, the subject is unwilling or unable to be seen by the investigator, medical records from primary care physician may be used. In addition, the Carolinas Comfort Scale™ QOL questionnaire may be answered over the phone to study personnel. In the event of these occurrences, subjects will not be compensated.

[figure not shown]
After the study has been completed no further study specific medical care will be provided and subjects will receive standard of care.

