14.3 Statistical Analysis Endpoints

14.3.1 Primary Endpoint

Incidence of hernia recurrence within 12 months will be calculated on the FAS subjects who reach the 12-month follow-up including any subject with hernia recurrence diagnosed within the 12-month period following surgery (even if the subject has withdrawn from the study before the 12-month assessment).

The primary endpoint will be summarized using count, percentage, and the corresponding 95% confidence interval. Sub-group analyses on primary endpoints will be performed according to study needs and will be described in the Statistical Analysis Plan and the Clinical Study Report.

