14.3.2 Secondary Endpoints

- Incidence of ADEs intra-operatively will be calculated on the FAS subjects who reach the corresponding time point, including any subject experiencing hernia recurrence, AEs or ADE within the corresponding follow-upperiod.
- Incidence of hernia recurrences will be calculated on the FAS subjects who reach the corresponding time point.
- Time to hernia recurrence, as well as time to AE occurrence analyses will be run using Kaplan Meier estimate and curve.
- Subject quality of life (QoL) questionnaires will be evaluated using the Carolinas Comfort
 Scale™ (Appendix B), and statistical analysis will follow the corresponding analysis guideline.
- Length of hospital stay will be summarized using count, mean, standard deviation, median, minimum, and maximum.

Subgroup analyses on secondary endpoints will be performed according to study needs and will be described in the statistical analysis plan and the clinical study report.

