CCS	Carolina Comfort Scale: it is a validated, disease-specific, quality of life (QOL) questionnaire developed for patients undergoing hernia repair.					
CE Mark	European Community Marking that indicates that the product (device) complies with the European Legislation and so can go to EU market.					
CI	Confidence Interval					
CIP	Clinical Investigation Plan (can be used synonymously with Protocol)					
Device Deficiency	Inadequacy of a medical device with respect to its identity, quality, durability, reliability, safety or performance. Note: Device deficiencies include malfunctions, use errors, and inadequate labeling.					
FAS	Full Analysis Set – An analysis set including any subjects enrolled and receiving study device					
Hernia recurrence	A clinically manifested bulge or a protrusion exacerbated by a Valsalva maneuver.					
IA	Interim Analysis					
IRB	Institutional Review Board					
ISO	International Organization for Standardization					

Version [Final v3.0]

Page 5 of 18

Term/Abbreviation	Definition
PMCF	Post market clinical follow up
PPAS	Per Protocol Analysis Set – An analysis set consisting of a subset of the full analysis set of subjects who meet the primary endpoint (12-month assessment) and who did not deviate (major) from the protocol
QOL	Quality of Life
SAE	 Serious Adverse Event - Adverse event that: a. Led to a death, b. Led to a serious deterioration in the health of the subject, that either resulted in: Resulted in a life-threatening illness or injury, or Resulted in a permanent impairment of a body structure or a body function, or In-patient or prolonged hospitalization, or Medical or surgical intervention to prevent life threatening illness or injury or permanent impairment to a body structure or a body function, or Led to fetal distress, fetal death or a congenital abnormality or birth defect. Note: Planned hospitalization for a pre-existing condition, or a procedure required by the CIP, without serious deterioration in health, is not considered a serious adverse event.
SADE	Serious Adverse Device Effect - Adverse device effect that has resulted in any of the consequences characteristic of a serious adverse event.
SAP	Statistical Analysis Plan
SAS	Safety Analysis Set is an analysis set including any subject pre-operatively eligible for the study and with skin incision, including those who are 'screen failure during surgery.
USA	United States of America

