7.8.2. Second Interim Analysis

A second interim analysis is planned to occur when all enrolled subjects complete the 12-month visit, to assess both primary and secondary endpoints, when possible.

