7.9. Evaluation of Objectives

Study objectives will be assessed through study endpoints measurement.

The primary endpoint is incidence of hernia recurrence within 12 months following Parietene[™] DS Composite Mesh use in ventral hernia repair.

Incidence of hernia recurrence within 12 months will be measured on the FAS subjects and using the following calculation formula:

[Subjects with Recurrence diagnosed within the first 12month following surgery]

[Subjects with Recurrence diagnosed within the first 12month following surgery + Subjects free of recurrence with a follow-up ≥12months]

A confirmatory analysis of primary endpoint will be run using Per Protocol Analysis Set.

Secondary endpoints

- Incidence of adverse device effects (ADEs) intra-operatively, at discharge, within 1 month, 3 months, 12 months, and 24 months following Parietene[™] DS Composite mesh use in ventral hernia repair will be primarily assessed based on FAS, and secondarily using PPAS and SAS.
- Incidence of hernia recurrence at 1, 3 and 24 months. The evaluation of hernia recurrence will be performed during a physical examination, using the formula described previously, according to the different time-points, and based on FAS and PPAS.
- Time to hernia recurrence and time to adverse device effect occurrence (from surgery time-point), will be assessed using Kaplan Meyer estimates. FAS and PPAS will be used for time to hernia recurrence, while FAS, PPAS and SAS will be used for time to ADE occurrence analysis. Time to Device-related AEs occurrence may also be assessed using Kaplan Meyer estimates.
- Carolinas Comfort Scale[™] QOL questionnaires completed pre-operatively and at 1, 12 and 24 months postoperatively will be analyzed using the Carolina Comfort Scale User Guide recommendations and programming code (see Appendix B), and based on FAS and on PPAS.

Several Subgroup analyses will be performed. Comparative analyses will be performed by hernia type (primary hernia versus incisional hernia) on overall subjects and on a subgroup of subjects with robotically assisted laparoscopic repair. Results of subjects operated with robotically assisted laparoscopic repair will also be compared with subjects operated with a traditional Laparoscopic procedure.

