7.12. Changes to Planned Analysis

Some minor changes were made in this SAP in regard to the statistical methodology as described in CIP v1.0 document. These changes are related to Analysis Sets definitions and the use of these analysis sets for endpoints assessment.

From CIP v1.0, analysis sets were defined as follows:

- the Full Analysis Set (FAS, including any subject enrolled and receiving study device) representing the primary analysis population,
- the Per Protocol Analysis Set [PPAS, a subset of the FAS of subjects who meet the primary endpoint (12month assessment) and who did not deviate (major) from the protocol], as confirmatory analysis and,
- the Safety Analysis Set (any subject with skin incision including those who are 'screen failure during surgery') for safety and efficacy analysis

From SAP v1.0, analysis sets are defined as follows:

- Full Analysis Set (FAS): including any subject enrolled and receiving study device, representing the primary analysis population, for Efficacy and Safety analyses.
- Per Protocol Analysis Set (PPAS): a subset of the FAS of subjects who meet the primary endpoint (12month assessment) and who did not deviate (major) from the protocol, as confirmatory analysis for Efficacy and Safety analyses,
- Safety Analysis Set (SAS): any subject pre-operatively eligible with skin incision including those who are 'screen failure during surgery', used for Safety analysis.

Any major change in planned analysis as described in this SAP would result in SAP amendment.

Validation level I will be applied for endpoints evaluated at the first interim analysis.

First interim analysis (Safety analysis at 3-months) will evaluate subject's disposition, screening data, demographics characteristics and occurrence of procedure or device-related AE occurring within 3-month from surgery (see IA#1 parameters in section 7.8.1.).

Validation level III will be applied for any endpoint evaluated during second interim analysis or final analysis.

Validation levels are defined as follows:

- Level I: The peer reviewer independently programs output and then compares the output with that generated by the original Statistical Programmer.
- Level II: The peer reviewer reviews the code; where appropriate, performs manual calculations or simple programming checks to verify the output.
- Level III: Original Statistical Programmer performs a visual inspection of the code and output to confirm functionality.

9. References

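### SAP 7.9 counts event-free subjects only with full 12- or 24-month follow-up, although visits may be 30 days early; coded literally, this shrinks the 24-month denominator and can inflate the recurrence rate

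*SAP*

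**What the plan says.** SAP 7.9 takes as numerator the subjects whose recurrence is diagnosed in the first 12 months. The denominator is "Subjects with Recurrence diagnosed within the first 12month following surgery + Subjects free of recurrence with a follow-up ≥12months". Recurrence at 1, 3 and 24 months is to be computed "using the formula described previously, according to the different time-points, and based on FAS and PPAS".

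The visits at which recurrence is assessed have windows. Protocol 10.4.4 is headed "12-Month and 24-Month Follow-up (+/- 30 Days) Visit". The schedules in Protocol 10.1 and SAP 5 give the same ±30 days, and ±14 days at 1 and 3 months. Both place study exit at the 24-month visit.

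Several passages suggest that the denominator is meant to follow visits:

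- Protocol 14.3.1: the 12-month incidence "will be calculated on the FAS subjects who reach the 12-month follow-up including any subject with hernia recurrence diagnosed within the 12-month period".
- Protocol 14.3.2: "Incidence of hernia recurrences will be calculated on the FAS subjects who reach the corresponding time point".
- The PPAS definition (SAP 2 and 7.1.3): "subjects who meet the primary endpoint (12-month assessment) and who did not deviate (major) from the protocol".
- SAP 7.8.2: "A second interim analysis is planned to occur when all enrolled subjects complete the 12-month visit".

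SAP 7.12 records the departures from the protocol's methods: "These changes are related to Analysis Sets definitions and the use of these analysis sets for endpoints assessment". It lists no change to the recurrence denominator. SAP 7.4 plans no imputation for recurrence. Neither document says that an in-window visit stands for its nominal time point, how many days make a month, or which date ends follow-up.

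**The concern.** A negative examination on day 340 or day 710 complies with the protocol but fails the printed follow-up condition. Coded as written, that subject leaves the denominator, while a subject diagnosed on the same day stays in both numerator and denominator. Exclusion then depends on outcome, and the rate is pushed up.

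A subject seen early at 12 months usually regains the required follow-up at the 24-month visit, so the final 12-month rate largely repairs itself. The 24-month rate cannot, because no later visit exists. The 12-month rate at the second interim has the same problem if follow-up runs to the last visit.

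At stake are the reported rate, its interval and the effective sample size. The SAP assigns its lightest validation level, the programmer's own visual check, to second-interim and final endpoints. A literal coding might therefore not be noticed.

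**Working it through.** **The plan's own figures.** Half-width = 1.96 × √(p(1−p)/100). For p = 3.5, 4.0, 4.5 and 5.2% this gives 3.60, 3.84, 4.06 and 4.35 points, matching the printed ±3.6, 3.8, 4.1 and 4.4. Enrolment: 100 / (1 − 0.20) = 125. The planned precision therefore assumes about 100 subjects in the 12-month denominator.

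**A count by hand at 24 months.** Take 100 subjects assessed in window, 5 with recurrence: 3 found earlier and 2 at the 24-month visit.

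- Half the visits late: 4 recurrences are diagnosed by the anniversary, and about 48 of the 95 event-free subjects are seen on or after it. Literal: 4/(4 + 48) = 7.7%. With all 100 in the denominator: 4/100 = 4.0%. Counting the late in-window recurrence too: 5/100 = 5.0%.
- All visits late: literal 3/(3 + 95) = 3.1%; all 100 in the denominator, 3.0%; late recurrences counted too, 5.0%.

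The denominator rule only pushes the rate up. A literal rate below 5% comes from the numerator limit, which excludes recurrences found in window after the anniversary.

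**Simulation inputs.** From the documents: N = 125, 20% attrition at 12 months, the ±30-day windows, and the 3.5–5.2% planning range. Assumed: true recurrence 4.5% at 12 months and 8% at 24; 30% attrition by 24 months; visit SD 15 days, truncated to the window; anniversaries at days 365 and 730; recurrence found only at scheduled visits.

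In the tables, events = literal rate × literal n. The corrected-denominator rate is events/88 at 24 months and events/100 at 12 months.

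24 months:

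| Visits on average | Before day 730 | Literal rate | Events | Denominator corrected |
|---|---|---|---|---|
| 7 days early | 65% | 19.1% on 35 | 6.7 | 7.6% on 88 |
| centred | 49% | 13.0% on 48 | 6.2 | 7.1% on 88 |
| 7 days late | 32% | 9.6% on 60 | 5.8 | 6.5% on 88 |
| 14 days late | 19% | 7.8% on 70 | 5.5 | 6.2% on 88 |

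If recurrences found in window after the anniversary also count, the rate is 8.7–8.9% on 88 in every row. Rough check of the centred row: completers 125 × 0.70 = 87.5; event-free and seen on or after day 730, 87.5 × 0.92 × 0.51 = 41.1; plus 6.2 events gives 47.3, close to 48.

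Half-width for the centred row: literal 1.96 × √(0.13 × 0.87/48) = 9.5 points; corrected 1.96 × √(0.071 × 0.929/88) = 5.4 points.

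12 months:

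| Visits on average | Second interim, literal | Events | Denominator corrected | Final analysis, literal |
|---|---|---|---|---|
| 7 days early | 9.5% on 37 | 3.5 | 3.5% on 100 | 3.8% |
| centred | 5.7% on 52 | 3.0 | 3.0% on 100 | 3.2% |
| 7 days late | 3.7% on 67 | 2.5 | 2.5% on 100 | 2.6% |
| 14 days late | 2.7% on 79 | 2.1 | 2.1% on 100 | 2.1% |

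The denominator rule moves the final 12-month rate by at most about 0.3 point here (3.8 − 3.5).

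**Sensitivity at 24 months.**

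- With 60% of recurrences found at unscheduled visits, the literal rate is 21.4 / 15.2 / 11.8 / 9.9% in the same row order, against 9.1–9.2% when in-window recurrences count.
- With centred visits and 30-day months (day 720), it is 8.1% on 67.
- With centred visits, true 24-month recurrence of 4.5–12% and attrition of 25–40%, it is 9.3–18.4%, against 5.0–13.6%.
- At 1 and 3 months the effect is under one event.

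**The case against.** The best defence is that the literal 24-month cutoff is not printed. SAP 7.9 gives a cutoff only for 12 months and refers to time points for the rest. SAP 7.8.1 speaks of subjects completing the 3-month time point, and SAP 5 describes the same milestone as completed visits. With the protocol wording, the PPAS definition and SAP 7.8.2, this makes a visit-based denominator the likely intent, and under it no in-window subject is lost. That stands as evidence of intent and keeps the severity down. It does not settle the matter, because the only printed formula is in elapsed time and carries no window.

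It is also fair that visit spread, 24-month recurrence, attrition and the share of unscheduled diagnoses are assumed. The planned Kaplan-Meier analysis does not use this denominator, and the endpoint analyses are descriptive. All of that stands.

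Two stronger readings are tempting, and the documents do not support them.

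- **That the final 12-month primary rate is understated.** With centred visits the literal rate is 3.2%, against 4.7% when in-window recurrences up to day 395 count. But the objective, endpoint and formula (Protocol 5.1.1, 5.2.1, 14.3.1; SAP 4.1, 7.9) consistently limit the event to 12 months. A day-380 diagnosis falls outside the stated endpoint; counting it would change the endpoint. With 60% unscheduled detection the literal final rates are 4.7 / 4.4 / 4.1 / 3.9%, around the assumed truth of 4.5%.
- **That subjects lost early would count as event-free**, because Protocol 10.12.5 does not call them lost until the end of the study. This requires treating an administrative exit date as recurrence follow-up, against Protocol 14.3.1's condition that subjects reach the 12-month follow-up. It is speculative, and one clause closes it.

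**Conclusion.** The point holds for the denominator. SAP 7.9 as printed conflicts with the visit windows and with the apparent visit-based intent elsewhere. Coded literally, it drops compliant event-free subjects and keeps recurrences. The damage is greatest at 24 months and at the second interim, and small for the final 12-month rate.

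Neither the size nor the net direction can be fixed in advance, because visit timing is not in the documents. Under the stated assumptions, with centred visits and scheduled detection only, the 24-month rate is about 13% on 48, against about 7% on 88 with the denominator corrected or about 9% on 88 if in-window recurrences after the anniversary also count. Against that last figure, the distortion shrinks with later visits and reverses at 14 days late (7.8% against 8.9%), because late in-window recurrences leave the numerator.

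Severity is minor to moderate: no test decision changes.

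**What to change.** State in SAP 7.9:

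1. A subject with no recurrence diagnosed by the time point counts in the denominator if recurrence was assessed at the in-window visit (from day 335 or day 700; the 14-days-early equivalent at 1 and 3 months) or at any later assessment. This includes a subject first diagnosed after the time point, so that inclusion does not depend on the later outcome.
2. Follow-up ends at the last recurrence assessment, not at the exit form or data cut.
3. The 12-month limit on the numerator stays as the primary definition. A sensitivity analysis adds recurrences first found at the in-window visit after the anniversary (to day 395 or day 760).
4. Kaplan-Meier stays as planned.

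The cost is a few sentences and a few lines of code before the analysis is run, with no new visits or data. Protocol 14.1 allows analysis changes to be recorded in the SAP and study report, and the numerator in Protocol 14.3.1 is unchanged. The downside is that some event-free subjects are counted with up to 30 days less than nominal follow-up. The main rate also still depends on visit timing through its numerator (7.6% to 6.2% across the 24-month rows above), which is why the sensitivity analysis should be reported beside it.

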5.2 Endpoints

5.2.1 Primary Endpoint

Incidence of hernia recurrence within 12-months following Parietene™ DS Composite Mesh use in ventral hernia repair.

Hernia recurrence is defined as: A clinically manifested bulge or a protrusion exacerbated by a Valsalva maneuver. The evaluation of hernia recurrence will be performed during a physical examination and confirmed per site standard of care if necessary.

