10.6 Conducting Remote Subject Follow-up Visits

When an in-person subject follow-up visit is unable to occur, alternative follow up may be utilized. Remote or phone follow-up, medical record review, or follow-up with other healthcare practitioner may be utilized for 1-month, 3-month, 12-month and 24-month visits.

Clinic Electronic Medical Records (EMR) or medical records from primary care physicians may be used to assess hernia recurrence/reoperation and adverse events. Assessments will take place by delegated study personnel via remote follow-up visit(s).

- Assessments will include:
- Hernia recurrence/reoperation
- Adverse events assessment
- The Carolinas Comfort Scale™ QOL questionnaire (MDT17051PDS Clinical Investigation Protocol, Section 17.2: Appendix B) may be answered over the phone/remote to study personnel as requested at 1-month, 12-month and 24-month follow-up intervals, exempting 3-month follow-up visit as per the Parietene™ DS Composite Mesh in Ventral Hernia Repair CIP v3.

If hernia or hernia reoccurrence is suspected, the subject will be instructed to return to the clinic or hospital for diagnosis by the surgeon through clinical assessment. This should be done at the discretion of the Principal Investigator.

Data collection from remote follow-up visits will be entered in the EMR and via Oracle Clinical Remote Data Capture (OC RDC).

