4.2. Secondary Objective

The secondary objective of this study is to assess clinical outcomes, within 24 months following the use of Parietene[™] DS Composite Mesh in ventral hernia repair.

Version [Final v3.0]

5. Investigation Plan

This study is a single arm, prospective, multi-center, observational, US post-market study to confirm the clinical safety and performance of Parietene[™] DS Composite Mesh in ventral hernia repair.

After IRB approvals, subjects who have signed an informed consent form (and who meet the eligibility criteria) and have received Parietene[™] DS composite mesh will be enrolled in the study. Subjects will undergo elective ventral hernia repair using Parietene[™] DS Composite Mesh and be evaluated pre-operatively, at the procedure, at discharge, within 1 month, 3 months, 12 months and 24 months post-surgery. Remote or phone follow-up, medical record review, or follow-up with other healthcare practitioner may be utilized for 1-month, 3-month, 12-month and 24-month visits due to COVID-19 related reasons as explained in the CIP v4.0 and the Addendum VA.

An interim analysis based on 30 subjects with complete 3-month visits to assess the short-term safety of the device will be used to support EU regulatory approval. Study enrollment will continue during interim analysis. The study will continue as a post market clinical follow up (PMCF) with extended follow-up of subjects to assess the mid (12 months) and long (24 months) term safety and performance of the device. The study will include a minimum of 125 subjects who will be followed 24 months post-surgery at a minimum of 4 USA sites. Subject participation in the study will last a maximum of 26 months and overall, the study is estimated to proceed for up to 38 months.

Procedure/Assessment	Screening (Day-30 to 0)	Operative (Day 0)	Discharge Assessment	1 Month (±14 days) Follow-up	3 Month (±14 days) Follow-up	12 months (±30 days) Follow-up	24 months (±30 days) Follow-up
	Can be combined			(Visit)	(Visit)	(Visit)	(Visit)
Eligibility criteria	X1	X1					
Informed consent	X ²						
Subject demographics	Х						
Pregnancy status	X1	X1					
Medical and abdominal surgical history and relevant risk factors	x						
Carolina Comfort Scale™ (Appendix B)	x			х		х	Х
Hernia defect description		Х					
Recurrence history if applicable		Х					
Date of surgery, Operative time		Х					
Anesthesia / ASA grade		Х					
Intraoperative wound contamination class		х					

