7.1.2. Clinical Investigation Plan (CIP) Deviations

Subjects with protocol deviations will be summarized and protocol deviations will be reported by type on overall FAS subjects and distinguishing minor and major protocol deviations/violations.

Major protocol deviations and violations will be defined and identified by the study team prior to run statistical analysis, based on protocol deviations listing provided by statistician.

Version [Final v3.0]

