Hernia recurrence will be assessed during physical examination at 1-month, 3-month, 12-month and 24-month assessment post-surgery. Remote follow-up visits due to COVID-19 related reasons may be performed: if hernia or hernia reoccurrence is suspected during a remote visit using questionnaires, the subject will be instructed to return to the clinic or hospital for diagnosis by the surgeon through clinical assessment. This process is fully accepted by scientific societies^{5,6,7,8,9}

7.10.Safety Evaluation

Safety will be assessed as the proportion of subjects with AE based on the FAS, PPAS and SAS; AE incidence will be reported overall, and according to:

- Relation to the procedure
- Relation to the device including anticipated and unanticipated ADEs,
- Severity,
- Seriousness.

PPDS Statistical Analysis Plan	
Version [Final v3.0] Page 16 of 18	Mectronic

Listing of AEs, SAEs, ADEs and SADEs, and UADEs will be provided based on FAS, PPAS and SAS, using the MEDRA coding system classification for AE terms, and including characteristics described previously and AE outcome.

7.11.Health Outcomes Analyses

Health outcomes analyses are already part of primary and secondary endpoints analyses, as described previously.

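### Subjects assessed remotely without an examination can count as recurrence-free at 12 and 24 months, and no planned output shows recurrence status by mode of assessment

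*SAP*

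**What the plan says.** **Method.** Protocol 5.2.1 states: "The evaluation of hernia recurrence will be performed during a physical examination and confirmed per site standard of care if necessary". SAP 7.9 also names physical examination, for the 1-, 3- and 24-month endpoint and again for all four visits.

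**Remote exception.** Protocol 10.6 allows phone contact, record review or another practitioner at all four visits when an in-person visit cannot occur, and adds that "medical records from primary care physicians may be used to assess hernia recurrence/reoperation and adverse events". Protocol 10.6.1 expects a deviation and accepts that the examination may go unrecorded. Protocol 10.4.4 has a separate route at 24 months, through primary care records after three attempts. On who is then examined, SAP 7.9 says "if hernia or hernia reoccurrence is suspected during a remote visit using questionnaires, the subject will be instructed to return to the clinic".

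**Estimator.** In SAP 7.9 the numerator is subjects with a recurrence diagnosed within 12 months. The denominator adds "Subjects free of recurrence with a follow-up" of at least 12 months. The 1-, 3- and 24-month rates are obtained "using the formula described previously, according to the different time-points".

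**Related outputs.** Under SAP 7.1.2 "protocol deviations will be reported by type on overall FAS subjects", split into minor and major. On grading, "Major protocol deviations and violations will be defined and identified by the study team prior to run statistical analysis". The per-protocol set (SAP 7.1.3) requires both the 12-month assessment and no major deviation. Kaplan-Meier estimates of time to recurrence are planned, with no censoring rule given.

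**The concern.** Recurrence is defined as a clinical sign, and the remote route examines only subjects already under suspicion. A subject reached by phone with no complaint, or whose records mention no hernia, is not examined, and no rule makes that subject non-evaluable. With enough follow-up time, the subject satisfies the recurrence-free term of the formula.

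The consequence runs one way: an undetected recurrence moves a subject from event to non-event, and the rate falls. The study is single-arm and descriptive, so no test result changes. The estimated rate is its main product, however, and it will be read beside the 3.5% to 5.2% reported for the predicate device. From the planned outputs a reader could not tell how far the 12- or 24-month rate rests on unexamined subjects.

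The texts also disagree on how wide the remote route is. SAP 5 allows it "due to COVID-19 related reasons as explained in the CIP v4.0 and the Addendum VA". Protocol 10.6 sets no such limit, and the visit headings in protocol 10.1 offer clinic or remote follow-up throughout. Protocol 10.6 leaves recall of suspected cases to the Principal Investigator's discretion; SAP 7.9 does not mention this.

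**Working it through.** **Inputs from the documents** (protocol 14.5, SAP 6): 12-month recurrence p of 3.5% to 5.2%, 100 evaluable subjects, 20% attrition, 125 enrolled.

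**Assumed inputs** (the documents give none): f, the share of subjects assessed remotely without examination; s, the share of their recurrences still detected; e, the share of recurrences already found in person earlier. Mode is taken as unrelated to recurrence.

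**1. The plan's own figures.** 100/(1 − 0.20) = 125. The half-width 1.96 × √(p(1 − p)/100) gives 3.60, 3.84, 4.06 and 4.35 points at 3.5%, 4.0%, 4.5% and 5.2%. The printed values are 3.6, 3.8, 4.1 and 4.4, so they reproduce.

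**2. Reported rate under the formula as written.** Rate = p × (1 − f(1 − e)(1 − s)). With p = 4.5% and e = 0:

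| f | s = 0 | s = 0.3 | s = 0.5 | s = 0.7 |
|---|---|---|---|---|
| 10% | 4.05% | 4.2% | 4.3% | 4.4% |
| 25% | 3.4% | 3.7% | 3.9% | 4.2% |
| 50% | 2.25% | 2.9% | 3.4% | 3.8% |

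For f = 25%: 4.5 × (1 − 0.25) = 3.375 and 4.5 × (1 − 0.25 × 0.5) = 3.94. If e = 30%, f = 25% gives 3.7% at s = 0 and 4.1% at s = 0.5. With s = 1 there is no loss.

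Over p from 3.5% to 5.2%, with e = 0, the downward shift runs from 3.5 × 0.10 × 0.3 = 0.1 points to 5.2 × 0.50 = 2.6 points. In every case it is below the planned half-width for that rate.

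**3. Which sensitivity analysis.** Take p = 4.5% and e = 30%, so 1.35% of subjects have a recurrence found early and 3.15% have one still to be found at the time point.

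- *Simple proportion among examined subjects, all early recurrences counted.* At f = 50%: (0.0135 + 0.0315 × 0.5)/(0.0135 + 0.0315 × 0.5 + 0.955 × 0.5) = 0.02925/0.50675 = 5.8%. This error of 1.3 points can exceed the one being checked.
- *Kaplan-Meier, censored at the last examination, early recurrences found at a scheduled examination.* 1 − (1 − 0.0135)(1 − 0.0315/0.9865) = 4.5% for any f, because remaining events and remaining subjects both shrink by (1 − f).
- *Limit of the Kaplan-Meier version.* If the early recurrences are instead all found at unscheduled visits after remote subjects have been censored, the risk set at f = 50% is 0.0135 + 0.5 × 0.9865 = 0.50675. The first step is then 0.0135/0.50675 = 2.66%, and the estimate is 1 − (1 − 0.0266)(1 − 0.0319) = 5.8%. The same sum gives 4.9% at f = 25% and 4.6% at f = 10%.

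**4. Precision among examined subjects.** At n = 75 the half-width is 4.16 points at 3.5% and 5.02 at 5.2%, with 75 × 0.035 = 2.6 to 75 × 0.052 = 3.9 expected recurrences. At n = 50 it is 5.09 to 6.15 points, with 1.8 to 2.6.

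**The case against.** **The plan already requires an examination.** It does, in SAP 7.9 itself, and a reader of the formula alone might wrongly infer that no method is prescribed. The gap is narrower: the remote exception gives no rule for unexamined negatives.

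**Deviation reporting will show the problem.** In part. Individually reported deviations, tabulated by type, should give an approximate count of remote visits. They do not show how many of those subjects counted as recurrence-free.

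**The per-protocol analysis handles it.** It may. A subject without an examination could be held to lack the 12-month assessment and leave the set however the deviation is graded. A reader might infer the opposite, that these subjects necessarily stay in because grading is left to the study team. The documents support neither reading, because both conditions are unsettled for a remote visit. The primary analysis is on the full analysis set in any case.

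**Remote assessment could also raise the rate.** A reader might infer this from the discretionary recall. The numerator, however, counts diagnosed recurrences, and suspected cases are to return for diagnosis by the surgeon. The texts give little basis for an upward error of any stated size.

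**The shift is smaller than the half-width, and events will be few.** Both are true, and they limit the urgency. The half-width describes sampling error; missed recurrences are a bias on top of it.

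**Conclusion.** The point stands as a gap in the analysis plan that should be closed. The formula admits unexamined remote negatives at 12 and 24 months, this can lower the rate if recurrences are missed, and no planned output would show it.

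The size cannot be known from the documents. Under the assumptions shown, a true 4.5% with 25% remote would be reported as about 3.4% (none of their recurrences detected) or 3.9% (half detected). The first falls just below the predicate range and the second stays inside it. If few visits were remote, or remote detection was good, the effect is negligible.

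A reader might go further and infer that the reported rate will be biased, or that a rate among examined subjects only is the right one. Neither follows. The remote share is not given, and an examined-only proportion has its own error.

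The difference in scope between SAP and protocol is visible in the texts, but Addendum VA was not available and may settle part of it. Confidence is medium.

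**What to change.** Keep the current formula as the primary analysis and add to SAP 7.9:

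1. **A count** of 12- and 24-month recurrence status by assessment mode: physical examination by the study or another practitioner; phone or records without examination.
2. **One sensitivity analysis** using the Kaplan-Meier estimate already planned.
   - Censor recurrence-free subjects at their last documented physical examination.
   - Count examination-confirmed recurrences when found.
   - Censor subjects recalled from a remote visit at their last examination before that visit, so that remote positives and negatives are treated alike.
   - For the 12-month figure, use examinations up to that visit only.
   - Place scheduled examinations at the nominal visit, with events ahead of censorings. On actual dates, subjects would drop out of the risk set through the ±30-day window: a recurrence found with 10 still uncensored would take 1/10 off the curve instead of about 1/100.
   - Report how many recurrences were first found at unscheduled visits.
3. **A statement before analysis** of whether a remote visit without examination meets the 12-month assessment condition of the per-protocol set, and how the deviation is graded.
4. **Reconciliation** of SAP 5 and 7.9 with protocol 10.1, 10.4.4, 10.6 and Addendum VA on when remote assessment is allowed and whether recall is discretionary.

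**Cost.** SAP wording, one table and one analysis; no new visits or procedures. Site queries may be needed to learn whether another practitioner examined the subject. The sensitivity analysis has a wider interval (about 4.2 to 5.0 points if 75 are examined) and few events. It assumes that mode is unrelated to recurrence, and it reads high if many recurrences surface at unscheduled visits. It therefore belongs beside the primary rate and should not replace it.
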